7.1.3. Visit 2 – 2-Week Follow-Up Visit (14-17 Days After Visit 1)

- Ensure that the participant continues to be eligible for the study and meets none of the participant withdrawal criteria as described in Section 7.5.
- Verify understanding of and compliance with protocol requirements for contraception.
- Collect a blood sample of approximately 15 mL for immunogenicity assessments.
- CCI
- Review the participant's e-diary data and collect the e-diary. Collect stop dates of any e-diary events ongoing on the last day that the e-diary was completed and record stop dates in the CRF.
- Complete the participant's source documents.
- Record nonstudy vaccinations and medications as described in Section 6.10.3.
- Record AEs as described in Section 8.8 and Section 9.
- The investigator or an authorized designee completes the CRF.

7.1.4. Visit 3 – 1-Month Follow-Up Visit (28-42 Days After Visit 1)

- Ensure that the participant continues to be eligible for the study and meets none of the
 participant withdrawal criteria as described in Section 7.5.
- Verify understanding of and compliance with protocol requirements for contraception.
- Collect a blood sample of approximately 15 mL for immunogenicity assessments.
- CCI

CCI
 Refer to
the SRM for further details.

Complete the participant's source documents.

Final Protocol Amendment 8, 27 March 2023

- Record nonstudy vaccinations and concomitant medications as described in Section 6.10.3.
- Record AEs as described in Section 8.8 and Section 9.
- The investigator or an authorized designee completes the CRF.

7.1.5. Visit 4 – 6-Month Follow-Up Telephone Contact (160-200 Days After Visit 1)

The 6-month telephone contact should be attempted for all participants who have received vaccination, unless they have withdrawn consent. The following procedures will be performed:

- Verify understanding of and compliance with protocol requirements for contraception.
- Complete the participant's source documents.
- Record concomitant medications as described in Section 6.10.3. Only concomitant medication taken to treat an AE will be recorded in the CRF.
- Record AEs as described in Section 8.8 and Section 9.
- The investigator or an authorized designee completes the CRF.

7.1.6. Visit 5 – Pre-Booster Screening (Days -7 to -2 Prior to Booster Vaccination)

Participants will be screened from 2 to 7 days prior to the booster vaccination to confirm that they meet eligibility (all of the inclusion criteria and none of the exclusion criteria) for the booster vaccination.

If the participant is found ineligible on the basis of laboratory assessment, the investigator may advise the participant of the results by telephone, and the participant will be withdrawn from further participation in the study. All eligible participants (without laboratory abnormalities) will proceed to Visit 6.

The following procedures will be performed:

- Obtain written informed consent before performing any study-specific procedures.
- Record the presence of chronic conditions and/or medical history of significance, including relevant surgical procedures, that have been diagnosed since Visit 1.

- Perform physical examination evaluating any clinically significant abnormalities
 within the following body systems: general appearance; skin; head, eyes, ears, nose,
 and throat; heart; lungs; abdomen; musculoskeletal; extremities; neurological; and
 lymph nodes. Abnormal results must be recorded on source documents and the
 physical examination page of the CRF.
- Measure vital signs, including weight, height, oral temperature, sitting blood pressure and pulse rate, and respiratory rate.
- Ensure and document that all of the inclusion criteria and none of the exclusion criteria are met (see Section 5).
- Obtain a blood sample (approximately 5 mL) for HIV, HBV, and HCV testing.
 Participants testing positive for HIV, acute or chronic HBV, or HCV will be withdrawn from further participation in the study.
- Collect an additional blood sample of approximately 25 mL.
- Complete the source documents.

Final Protocol Amendment 8, 27 March 2023

- Record nonstudy vaccinations and concomitant medications as described in Section 6.10.3.
- Record AEs as described in Section 8.8 and Section 9.
- The investigator or an authorized designee completes the CRF.

7.1.7. Visit 6 – Booster Vaccination (Approximately 2 Years After Visit 1)

- Ensure that the participant is eligible for the booster vaccination and meets none of the temporary delay criteria as described in Section 5.8.
- Review screening laboratory results.
- Prior to vaccination, measure oral temperature.
- Prior to vaccination, perform a urine pregnancy test for female participants of childbearing potential.
- Prior to vaccination, collect a blood sample of approximately 140 mL.
- Verify understanding of and compliance with protocol requirements for contraception.

- Use the IRT to assign investigational product container number and prepare and administer a single preferably of the nondominant arm. Please refer to the IPM for further instruction on this process.
- Site staff must observe the participant for at least 30 minutes after investigational product administration for any acute reactions. Record any acute reactions in the participant's source documents and on the AE page of the CRF, and on an SAE form as applicable.
- Issue a measuring device to measure local reactions and a digital thermometer for recording daily temperatures and provide instructions on their use.
- Issue the participant an e-diary and provide instructions on its completion. Ask the
 participant to complete the e-diary from Day 1 to Day 7, with Day 1 being the day of
 vaccination.
- Ask the participant to contact the site staff or investigator immediately if prompted by the e-diary from Day 1 to Day 7 following vaccination to determine if an unscheduled visit is required (eg, redness or swelling at the injection site measuring ≥21 measuring device units [≥10.5 cm]).
- Remind participants that study staff may contact them to obtain additional information on Grade 3 events entered into the e-diary.
- Ask the participant to contact the site staff or investigator if a medically attended event (eg, emergency room) or hospitalization occurs.
- Complete the participant's source documents.
- Record nonstudy vaccinations and concomitant medications as described in Section 6.10.3.
- Record AEs as described in Section 8.8 and Section 9.
- The investigator or an authorized designee completes the CRF and updates the investigational product accountability records.
- Designated site staff will review e-diary data online at frequent intervals for the 7 days following vaccination to evaluate participant compliance and as part of the ongoing safety review.

7.1.8. Visit 7 – 1-Month Booster Vaccination Follow-Up Visit (28-42 Days After Visit 6)

- Ensure that the participant continues to be eligible for the study and meets none of the participant withdrawal criteria as described in Section 7.5.
- Verify understanding of and compliance with protocol requirements for contraception.
- Collect a blood sample of approximately 140 mL.
- Review the participant's e-diary data and collect the e-diary. Collect stop dates of any e-diary events ongoing on the last day that the e-diary was completed and record stop dates in the CRF.
- Complete the participant's source documents.
- Record nonstudy vaccinations and concomitant medications as described in Section 6.10.3.
- Record AEs as described in Section 8.8 and Section 9.
- The investigator or an authorized designee completes the CRF.

7.1.9. Visit 8 – 3-Month Booster Vaccination Follow-Up Visit (84-126 Days After Visit 6)

- Ensure that the participant continues to be eligible for the study and meets none of the
 participant withdrawal criteria as described in Section 7.5.
- Verify understanding of and compliance with protocol requirements for contraception.
- Collect a blood sample of approximately 140 mL.
- Complete the participant's source documents.
- Record concomitant medications as described in Section 6.10.3. Only concomitant medication taken to treat an AE will be recorded in the CRF.
- Record AEs as described in Section 8.8 and Section 9.
- The investigator or an authorized designee completes the CRF.

7.1.10. Visit 9 – 6-Month Booster Vaccination Follow-Up Visit (160-200 Days After Visit 6)

- Ensure that the participant continues to be eligible for the study and meets none of the participant withdrawal criteria as described in Section 7.5.
- Verify understanding of and compliance with protocol requirements for contraception.
- Collect a blood sample of approximately 140 mL.
- Complete the participant's source documents.
- Record concomitant medications as described in Section 6.10.3. Only concomitant medications taken to treat an AE will be recorded in the CRF.
- Record AEs as described in Section 8.8 and Section 9.
- The investigator or an authorized designee completes the CRF.

7.1.11. Visit 10 – Blood Draw Follow-Up Visit (14-184 Days After Visit 9)

- Obtain written informed consent before performing any study-specific procedures.
- Ensure that the participant continues to be eligible for the study and meets none of the
 participant withdrawal criteria as described in Section 7.5.
- Verify understanding of and compliance with protocol requirements for contraception.
- Collect a blood sample of approximately 125 mL.
- Complete the participant's source documents.
- Record concomitant medications as described in Section 6.10.3. Only concomitant medications taken to treat an AE will be recorded in the CRF.
- Record AEs as described in Section 8.8 and Section 9.
- The investigator or an authorized designee completes the CRF.

7.2. Stage 2 and 3 Study Procedures – Maternal Participants

If, because of a medical situation (such as disease outbreak or pandemic), study visits cannot be conducted in person at the study site, visit procedures should be conducted remotely or via telephone, as is feasible.

7.2.1. Visit 0 - Screening (Days -14 to -2 Prior to Vaccination)

Participants will be screened from 2 to 14 days prior to administration of the investigational product to confirm that they meet eligibility (all of the inclusion and none of the exclusion) criteria for the study.

For Stage 2 sentinel-cohort participants only: In the 14-day screening period, retesting of the screening blood/chemistry laboratory parameters will be allowed at the discretion of the investigator if the investigator believes the results to be erroneous. In this circumstance, participants will return for a second screening visit within the 14-day screening period to reevaluate the screening laboratory parameters (see Section 7.2.2).

If the participant is found ineligible for the study on the basis of screening laboratory assessment and repeat testing is not warranted, the investigator may advise the participant of the results by telephone, and the participant will be withdrawn from further participation in the study. All eligible participants will proceed to Visit 1.

The following procedures will be performed:

- Obtain written informed consent before performing any study-specific procedures.
- Assign a single participant identifier using the IRT system.
- Obtain and record the participant demography (including date of birth, sex, race, and ethnicity). The complete date of birth (dd-mmm-yyyy) will be collected to critically evaluate the immune response and safety profile by age.
- Obtain and record current alcohol and tobacco usage.
- Obtain and record any medical and obstetric history of clinical significance including history from prior and current pregnancy(ies). Refer to the SRM for further details.
- Record the last normal menstrual period (LMP) and estimated date of delivery (EDD).
- Measure vital signs, including weight, height, oral temperature, sitting blood pressure and pulse rate, and respiratory rate.
- Perform physical examination evaluating any clinically significant abnormalities
 within the following body systems: general appearance; skin; head, eyes, ears, nose,
 and throat; heart; lungs; abdomen; musculoskeletal; extremities; neurological; and
 lymph nodes. Abnormal results must be recorded on source documents and the
 physical examination page of the CRF.
- Perform obstetric examination including but not limited to scars from previous deliveries, fundal height, fetal heart tones, and fetal movement.

- Perform obstetric ultrasound and/or record findings to confirm singleton pregnancy and rule out fetal abnormalities.
- Ensure and document that all of the inclusion criteria and none of the exclusion criteria are met (see Section 5).
- Obtain blood sample (approximately 10 mL) for HBV, HCV, HIV, and syphilis testing. Participants testing positive for HIV, acute or chronic HBV, HCV, or syphilis will not be eligible for randomization.
- Stage 2 sentinel cohort only: Obtain a blood sample (approximately 10 mL) for hematology and blood chemistry assessments. The following parameters will be assessed:
 - Hematology: hemoglobin, hematocrit, red blood cell (RBC) count, white blood cell (WBC) count with differential, and platelets.
 - Blood chemistries: alanine aminotransferase (ALT), aspartate aminotransferase (AST), alkaline phosphatase, total bilirubin, blood urea nitrogen (BUN), and creatinine.
- Obtain urine sample for glucose and protein testing (urine dipstick).
- Complete the source documents.

- Record nonstudy vaccinations and medications (including antibiotic medications) as described in Section 6.10.3.
- Record AEs as described in Section 8.8 and Section 9.
- The investigator or an authorized designee completes the CRF.

7.2.2. Visit 0 – Rescreening Visit (Days -14 to -2 Prior to Vaccination) – Stage 2 Sentinel-Cohort Participants Only

If abnormal blood/chemistry laboratory parameters are reported at Visit 0 and the investigator believes the results to be erroneous, a second screening visit may be conducted. The following information will be collected and the following assessments will be made at a rescreening visit:

- Ensure and document that all of the inclusion criteria and none of the exclusion criteria are met (see Section 5).
- Obtain a blood sample (approximately 10 mL) for analysis of hematology and blood chemistry assessments (see Section 8.5.3). Retest only abnormal laboratory parameters from Visit 0.

Complete the source documents.

Final Protocol Amendment 8, 27 March 2023

- Record nonstudy vaccinations and medications as described in Section 6.10.3.
- Record AEs as described in Section 8.8 and Section 9.
- The investigator or an authorized designee completes the CRF.

If the participant is subsequently found ineligible for the study on the basis of hematology and/or blood chemistry laboratory assessment, the investigator may advise the participant of the results by telephone, and the participant will be withdrawn from further participation in the study. All eligible participants will proceed to Visit 1.

7.2.3. Visit 1 – Vaccination (Day 1) Visit

- Review laboratory results.
- Ensure that the participant continues to be eligible for the study, meets none of the
 participant withdrawal criteria as described in Section 7.5, and meets none of the
 temporary delay criteria as described in Section 5.8.
- Prior to vaccination, measure vital signs, including weight, oral temperature, sitting blood pressure and pulse rate, and respiratory rate.
- Perform a targeted physical examination, evaluating any clinically significant
 abnormalities based on history and the participant's self-reported symptoms or
 complaints since the last visit. Abnormal results, including those that indicate
 worsening of medical history conditions, must be recorded on source documents
 and the AE CRF (with recording of time relative to vaccination) as appropriate.
- Perform obstetric examination including but not limited to fundal height, fetal heart tones, and fetal movement.
- Obtain urine sample for glucose and protein testing (urine dipstick).
- Issue the participant an e-diary and provide instructions on its completion. Ensure
 that the participant records a baseline assessment of prompted systemic events in the
 e-diary prior to vaccination.
- Prior to vaccination, collect a blood sample of approximately 15 mL for immunogenicity assessments.

	CCI	
•	CCI	
•		

Refer to the SRM for further details.

- A blinded site staff member will use the IRT system to obtain the participant's
 randomization number. An unblinded site staff member will use the IRT to assign
 investigational product container number and will prepare the investigational product
 and deliver it to the investigational product administrator. Please refer to the IPM for
 further instruction on this process.
- The unblinded administrator administers a single , preferably of the nondominant arm.
- Blinded site staff must observe the participant for at least 30 minutes after investigational product administration for any acute reactions. Record any acute reactions in the participant's source documents and on the AE page of the CRF, and on an SAE form as applicable.
- Issue a measuring device to measure local reactions and a digital thermometer for recording daily temperatures and provide instructions on their use.
- Ask the participant to complete the e-diary from Day 1 to Day 7 (Day 1 is the day of vaccination).
- Ask the participant to contact the site staff or investigator immediately if prompted by the e-diary from Day 1 to Day 7 following vaccination to determine if an unscheduled visit is required (eg, redness or swelling at the injection site measuring ≥21 measuring device units [≥10.5 cm]).
- Remind participants that study staff may contact them to obtain additional information on Grade 3 events entered into the e-diary.
- Ask the participant to contact the site staff or investigator if a medically attended event (eg, emergency room) or hospitalization occurs.
- Complete the participant's source documents.
- Record nonstudy vaccinations and concomitant medications (including antibiotic medications) as described in Section 6.10.3.
- Record AEs as described in Section 8.8 and Section 9.
- The investigator or an authorized designee completes the CRF, and an unblinded site staff member updates the investigational product accountability records.
- Designated site staff will review e-diary data online at frequent intervals for the 7 days following vaccination to evaluate participant compliance and as part of the ongoing safety review.

7.2.4. Visit 2 – 2-Week Follow-Up Visit (14-17 Days After Visit 1)

If delivery occurs before this visit, this visit will not be conducted; however, the hematology and chemistry assessments planned to be collected at this visit should be conducted at the delivery visit, if possible. For the other procedures to be conducted at delivery, see Section 7.2.6.

- Ensure that the participant continues to be eligible for the study and meets none of the participant withdrawal criteria as described in Section 7.5.
- Measure vital signs, including weight, oral temperature, sitting blood pressure and pulse rate, and respiratory rate.
- Perform a targeted physical examination, evaluating any clinically significant
 abnormalities based on history and the participant's self-reported symptoms or
 complaints since the last visit. Abnormal results, including those that indicate
 worsening of medical history conditions, must be recorded on source documents
 and the AE CRF (with recording of time relative to vaccination) as appropriate.
- Perform obstetric examination including but not limited to fundal height, fetal heart tones, and fetal movement.
- Collect a blood sample of approximately 15 mL for immunogenicity assessments.
- Stage 2 sentinel cohort only: Obtain a blood sample (approximately 10 mL) for hematology and blood chemistry assessments. The following parameters will be assessed:
 - Hematology: hemoglobin, hematocrit, RBC count, WBC count with differential, and platelets.
 - Blood chemistries: ALT, AST, alkaline phosphatase, total bilirubin, BUN, and creatinine.
 - Retesting of abnormal laboratory parameters will be allowed at the discretion of the investigator if the investigator believes the results to be erroneous.
- Review the participant's e-diary data and collect the e-diary. Collect stop dates of any e-diary events ongoing on the last day that the e-diary was completed and record stop dates in the CRF.
- Complete the participant's source documents.
- Record nonstudy vaccinations and concomitant medications (including antibiotic medications) as described in Section 6.10.3.
- Record AEs as described in Section 8.8 and Section 9.
- The investigator or an authorized designee completes the CRF.

7.2.5. Visit 3 – 1-Month Follow-Up Visit (28-42 Days After Visit 1)

If delivery occurs before this visit, please conduct the delivery visit instead. For procedures to be conducted at delivery, see Section 7.2.6.

- Ensure that the participant continues to be eligible for the study and meets none of the participant withdrawal criteria as described in Section 7.5.
- Measure vital signs, including weight, oral temperature, sitting blood pressure and pulse rate, and respiratory rate.
- Perform a targeted physical examination, evaluating any clinically significant
 abnormalities based on history and the participant's self-reported symptoms or
 complaints since the last visit. Abnormal results, including those that indicate
 worsening of medical history conditions, must be recorded on source documents
 and the AE CRF (with recording of time relative to vaccination) as appropriate.
- Perform obstetric examination including but not limited to fundal height, fetal heart tones, and fetal movement.
- Collect a blood sample of approximately 15 mL for immunogenicity assessments.
- . CC
- Complete the participant's source documents.
- Record nonstudy vaccinations and medications (including antibiotic medications) as described in Section 6.10.3.
- Record AEs as described in Section 8.8 and Section 9.
- The investigator or an authorized designee completes the CRF.

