- a. Visits at 2 weeks and 1 month after vaccination will not be performed if delivery occurs before the visits. In that case, hematology, and chemistry assessments due at the 2-week visit should be conducted at the delivery visit. Once delivery occurs, the visit windows are calculated based on delivery date.
- b. If abnormal laboratory values (as defined in Screening, Section 7.2.1, and in Section 8.5.3) are reported at Visit 0/Visit 2 and the investigator believes the results to be erroneous, the abnormal laboratory parameters may be retested.
- c. Vital signs include weight, height (only required at Visit 0), oral temperature, sitting blood pressure and pulse rate, and respiratory rate.
- d. Only concomitant medication taken to treat an adverse event will be recorded in the case report form.
- CCI
- f. Blood sample may be collected up to 72 hours after delivery.
- g. Participants will provide (in an e-diary) a baseline assessment of prompted systemic events prior to vaccination and participants will record (in an e-diary) reactogenicity events within a fixed time window each day for 7 days following vaccination. Remind participants that study staff may contact them to obtain additional information on Grade 3 events entered into the e-diary. Ask participants to contact the investigator or site staff immediately if they are prompted by the e-diary from Day 1 to Day 7 following vaccination to determine if an unscheduled visit is required (see Section 7.4).
- h. Designated site staff will review e diary data online at frequent intervals for the 7 days following vaccination to evaluate participant compliance and as part of the ongoing safety review.
- i. Only adverse events occurring up to 48 hours after each blood draw that are related to study procedures must be recorded in the case report form.

Stages 2 and 3 – Schedule o	f Activities	for Infant Par	ticipants				
Visit Number	1	2	3	4	5	6	7
Equivalent Visit Number for Maternal Participants	4	5	6	7	N/A	8	9
Visit Description	Delivery	1-Week Postdelivery Follow-Up	6-Week Postdelivery Follow-Up	14-Week Postdelivery Follow-Up	18-Week Postdelivery Follow-Up	6-Month Postdelivery Follow-Up	12-Month Postdelivery Follow-Up
Visit Window (Days)	Varies	7-10 Days After Visit 1	35-49 Days After Visit 1	80-100 Days After Visit 1	119-133 Days After Visit 1	160-200 Days After Visit 1	365-385 Days After Visit 1
Type of Visit	Hospital	Phone Call	Clinic	Clinic	Clinic	Phone Call	Clinic

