- Proportions of maternal participants reporting prompted local reactions within 7 days following administration of investigational product (pain at the injection site, redness, and swelling).
- Proportions of maternal participants reporting prompted systemic events within 7 days following administration of investigational product (fever, nausea/vomiting, diarrhea, headache, fatigue/tiredness, muscle pain, and joint pain).
- Proportions of maternal participants reporting AEs through 1 month after administration of investigational product.
- Proportions of maternal participants with SAEs, MAEs, and obstetric complications (prepartum, intrapartum, and postpartum) throughout the study (Visit 1 through the 12-month postdelivery study visit).
- Proportions of maternal participants with each delivery outcome (live birth, delivery mode).

3.1.6. Primary Safety Endpoints (Infant Participants): Stages 2 and 3

- Proportions of infant participants with specific birth outcomes.
- Proportions of infant participants with AEs from birth to 6 weeks of age.
- Proportions of infant participants with SAEs, AEs of special interest (major congenital anomalies, developmental delay, and suspected or confirmed GBS infection), and MAEs through 12 months of age.

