4. STUDY DESIGN

This is a Phase 1/2, randomized, placebo-controlled, observer-blinded study to evaluate the safety, tolerability, and immunogenicity of a multivalent GBS vaccine in healthy 18- to 40-year-old nonpregnant women as well as pregnant women and their infants. Participants in Stage 2 will be vaccinated between 27 0/7 and 35 6/7 weeks' gestation and participants in Stage 3 will be vaccinated between 24 0/7 and 35 6/7 weeks' gestation.

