9.1.4. Time Period and Frequency for Collecting AE/SAE Information

The time period for actively eliciting and collecting AEs and SAEs ("active collection period") for each nonpregnant participant begins from the time the participant provides informed consent, which is obtained before the participant's participation in the study (ie, before undergoing any study-related procedure and/or receiving study intervention), through and including Visit 3, and from Visit 5 to Visit 7. Between Visit 3 and Visit 4, and between Visit 7 and Visit 10, only SAEs (including hospitalizations) and MAEs will be reported.

The time period for actively eliciting and collecting AEs and SAEs ("active collection period") for each maternal participant including her fetus begins from the time the maternal participant provides informed consent, which is obtained before the participant's participation in the study (ie, before undergoing any study-related procedure and/or receiving study intervention), through and including a minimum of 28 calendar days (except as indicated below) after the last administration of the study intervention.

Follow-up by the investigator continues throughout and after the active collection period and until the AE or SAE or its sequelae resolve or stabilize at a level acceptable to the investigator.

For participants who are screen failures, the active collection period ends when screen failure status is determined.

If the participant withdraws from the study and also withdraws consent for the collection of future information, the active collection period ends when consent is withdrawn.

If a participant permanently discontinues or temporarily discontinues study intervention because of an AE or SAE, the AE or SAE must be recorded on the CRF and the SAE reported using the Vaccine SAE Reporting Form.

Investigators are not obligated to actively seek AEs or SAEs after the participant has concluded study participation. However, if the investigator learns of any SAE, including a death, at any time after a participant has completed the study, and he/she considers the event to be reasonably related to the study intervention, the investigator must promptly report the SAE to Pfizer using the Vaccine SAE Reporting Form.

9.1.4.1. Stage 1

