9.1.4.2. Stages 2 and 3 – Maternal Participants

In this study, the investigator and site staff will ensure the active elicitation and collection of AEs and SAEs through Visit 3. At 1 week following delivery (Visit 5), the participant will be contacted by telephone to inquire about MAEs and SAEs, including hospitalizations, since Visit 3. At all subsequent visits (Visits 6, 7, 8, and 9), only MAEs and SAEs, including hospitalizations, will be reported.

Immediate AEs will be reported as detailed in Section 8.8.2.

In addition, AEs occurring up to 48 hours after the Visit 4, Visit 6, and Visit 9 blood draws that are related to study procedures must be reported in the CRF.

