# 6.1.2.4. Proportion of Maternal Participants Reporting AEs Through 1 Month After Administration of the Investigational Product

Endpoints: AEs experienced by maternal participants (Stages 2 and 3).

- Analysis time points: Day 1 to 1 month after vaccination.
- Analysis population: Safety population for maternal participants (Stages 2 and 3).
- Analysis methodology: Descriptive summary statistics.
- Supporting objective: Primary safety objective.

- Raw data: The number of participants with AEs (n), proportion, and associated 2-sided exact 95% CI will be presented for any AEs, SAEs, immediate AEs, severe AEs, related AEs, MAEs, and AEs leading to withdrawal, by vaccine group. Additionally, the number of participants with AEs (n), proportion, and associated 2-sided exact 95% CI will be presented for any AE, each SOC, and each preferred term within SOC, by vaccine group.
- Tier 2 AEs: The number of participants with AEs (n), proportion, risk difference, and associated 2-sided exact 95% CI will be presented for each preferred term.

Figures: None.

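### For women who deliver before Visit 3, the protocol's AE collection rules conflict, and no scheduled contact clearly elicits nonserious, non-medically-attended AEs through the 1-month primary endpoint window

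*Protocol*

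**What the plan says.** The primary endpoint in Protocol 3.1.5 is "Proportions of maternal participants reporting AEs through 1 month after administration of investigational product". SAP 6.1.2.4 analyses it in the maternal safety population: "Analysis time points: Day 1 to 1 month after vaccination".

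Several places govern how long these events are collected:

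- Protocol 9.1.4 has active collection run from consent "through and including a minimum of 28 calendar days (except as indicated below) after the last administration of the study intervention".
- Protocol 9.1.4.2 has sites actively elicit AEs up to Visit 3, and Table 8 gives consent to Visit 3 as the period for nonserious AEs. SAEs and MAEs continue to Visit 9.
- On Visit 3, planned 28 to 42 days after vaccination, Protocol 7.2.5 says: "If delivery occurs before this visit, please conduct the delivery visit instead". Footnote a of the maternal schedule (Protocol 1.2) likewise drops Visits 2 and 3 after delivery and counts later windows from the delivery date.
- In that schedule the AE row at Visits 4, 6 and 9 carries footnote i: "Only adverse events occurring up to 48 hours after each blood draw that are related to study procedures must be recorded". Visit 5 has no AE entry.
- At Visit 5, a week after delivery, 9.1.4.2 says that "the participant will be contacted by telephone to inquire about MAEs and SAEs, including hospitalizations, since Visit 3".

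On vaccination timing, Protocol 4 states that "Participants in Stage 2 will be vaccinated between 27 0/7 and 35 6/7 weeks" of gestation and that "participants in Stage 3 will be vaccinated between 24 0/7 and 35 6/7 weeks".

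**The concern.** A woman who delivers before Visit 3 has no Visit 3, so the event that closes her nonserious AE collection under 9.1.4.2 and Table 8 never happens. Footnote i narrows what is recorded at her delivery visit. Her Visit 5 call is confined to MAEs and SAEs and refers back to a visit she did not have. She still counts in the denominator of a proportion meant to cover a full month.

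The plan foresees early delivery elsewhere. Missed Visit 2 laboratory tests move to the delivery visit (Protocol 7.2.4), and a delivery blood sample can stand in for the 1-month sample (SAP 4.1.2). There is no counterpart for AEs.

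At stake is the completeness of a primary safety endpoint that is read as a descriptive proportion per group, chiefly in women vaccinated late in the permitted range. Sites could also resolve the conflict in different ways.

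**Working it through.** The documents give no figure for this problem, so there is nothing of the plan's to reproduce. The check has three steps.

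**1. Which contacts ask for nonserious, non-medically-attended AEs if delivery comes first?**

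| Contact | Rule | Clearly elicits them? |
|---|---|---|
| Visit 3 | Not held (7.2.5, footnote a) | No |
| Visit 4, delivery | Procedure-related within 48 hours (footnote i); procedure list points to Section 9 | Unclear |
| Visit 5 call | MAEs and SAEs (9.1.4.2); no AE entry in schedule; procedure list points to Section 9 | Unclear |
| Visit 6, 35–49 days after delivery | As Visit 4, plus a targeted examination | Examination findings only |

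The pointers to Section 9 lead both to the 28-day minimum in 9.1.4 and to the Visit 3 limit in 9.1.4.2, so they do not settle the matter.

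**2. Who is affected?** Vaccination at 35 6/7 weeks puts Day 28 at 39 6/7 and the close of the Visit 3 window, Day 42, at 41 6/7. Delivery at 37 0/7 precedes Day 28 only if vaccination was after 33 0/7 (37 0/7 minus 4 weeks). Delivery at 39 0/7 does so only if vaccination was after 35 0/7. The exposure therefore lies mainly with late vaccination, plus preterm deliveries.

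**3. How many, and how much?** Assumptions not in the documents: gestational age at delivery is normal with distribution function F, mean 38.5 to 39.5 weeks and SD 1.3 to 2.0, conditional on being undelivered at vaccination; vaccination is uniform over the permitted range. With g the gestational age at vaccination in days,

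p(g) = [F(g+28) − F(g)] / [1 − F(g)].

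Example with mean 39 (273 days), SD 1.5 (10.5 days) and g = 35 6/7 (251 days): F(279) = Φ(0.571) = 0.716 and F(251) = Φ(−2.095) = 0.018, so p = (0.716 − 0.018)/0.982 = 0.711.

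| Mean / SD (weeks) | p at 33 0/7 | p at 35 6/7 | Stage 2 average (of 360) | Stage 3 average (of 216) | Days lost per affected woman |
|---|---|---|---|---|---|
| 38.5 / 2.0 | 22.4% | 72.6% | 18.5% (67) | 13.9% (30) | 10.0 |
| 39.0 / 2.0 | 15.8% | 64.5% | 14.7% (53) | 11.0% (24) | 9.4 |
| 39.0 / 1.5 | 9.1% | 71.1% | 13.0% (47) | 9.7% (21) | 8.0 |
| 39.5 / 1.3 | 2.7% | 60.7% | 8.4% (30) | 6.3% (14) | 6.4 |

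Days lost are those between delivery and Day 28.

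For the endpoint, assume a true 28-day risk of 20% with constant hazard h = −ln(0.8)/28 = 0.00797 per day. A woman followed for t days then shows an event with probability 1 − exp(−ht). Averaging over delivery dates gives the observed risk across the four scenarios:

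| Elicitation ends at | Stage 2 | Stage 3 | Vaccinated at 35 6/7 |
|---|---|---|---|
| Delivery | 18.7–19.6% | 19.1–19.7% | 13.7–16.7% |
| Last visit held (Visit 2 at Day 14, otherwise Visit 1) | 17.7–19.1% | 18.3–19.3% | 9.9–13.2% |

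The stage-wide understatement is thus 0.3 to 2.3 percentage points. The model treats every AE after the cut-off as lost. MAEs, SAEs and other captured events would make the loss smaller, and so would AEs that cluster soon after vaccination. Clustering after delivery would make it larger.

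**The case against.** The best defence is that the 28-day minimum survives delivery. The exception in 9.1.4 can be read as meaning the two cases named later in that section, screen failure and withdrawal of consent. Protocol 8.8.1 requires questioning about AEs throughout the active collection period of 9.1.4, and the Visit 4, 5 and 6 procedure lists send the site to Section 9. This reading is tenable. A reader might infer from the schedule that elicitation stops at delivery, but no section says so; 7.2.5 only substitutes one visit for another. What the defence cannot do is remove 9.1.4.2, Table 8 and footnote i, which are more specific and point the other way.

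A reader might also infer that nonserious AEs after delivery go uncollected altogether. They do not. An MAE is by definition nonserious (8.8.3) and is collected to Visit 9. Spontaneously reported and directly observed AEs are recorded (9.1.2). Visit 6 findings from the targeted examination go on the AE form with their timing relative to vaccination (7.2.8). Postpartum obstetric complications are a separate primary endpoint. This stands and narrows the exposed class considerably.

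A third inference, that the vaccine-placebo contrast is biased, is also unsupported. Both arms follow the same rule, so a difference would require vaccination to shift delivery timing.

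Finally, the effect is small beside sampling error: at an observed 20%, the exact 95% interval is about 9–36% for 40 women and 13–29% for 108. The exclusion of women with prior preterm delivery or signs of premature labor (5.5) makes the early end of the delivery range less likely. Both points stand and limit the priority, but not the case for a clear rule on a primary endpoint.

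**Conclusion.** The point holds as an unreconciled conflict with a risk of under-ascertainment, not as an established truncation. Under the specific maternal rules, nonserious, non-medically-attended AEs between the last visit held and Day 28 are not clearly elicited in women who deliver before Visit 3, and the SAP does not say how these women count.

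Under the stated assumptions the expected effect is modest over a whole stage and material only for women vaccinated near the upper gestational-age limit. Uniform timing is more plausible in Stage 3, where enrollment is monitored for spread across gestational age, than in Stage 2, where no such rule is given. The counts cover delivery before Day 28 only; a woman who delivers between Day 28 and Day 42 before attending also misses Visit 3. No sample size changes. The correction is worth making because it is cheap and concerns a primary endpoint.

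**What to change.** **Protocol.** Reconcile 9.1.4 with 9.1.4.2, Table 8 and schedule footnotes a and i. State that, for women who deliver before Visit 3, nonserious AEs are elicited through 28 days after vaccination at the existing Visit 4, 5 and 6 contacts. Visit 6 is at least 35 days after delivery and so always falls beyond Day 28. Reword the Visit 5 question to refer to the last visit held.

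**SAP 6.1.2.4.** Report by vaccine group the number of women without Visit 3. Add a supplementary AE proportion among women with at least 28 days of elicitation, labelled as conditional on not delivering early, since that selects on an event after randomization. Keep the full safety-population analysis as the main one.

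**Cost.** Wording in two documents and one additional table; no new visits. Reported AE rates may rise slightly. Women already past this point keep the ascertainment they had, so the two rules must be distinguished in reporting. Amendment 8 describes the Stage 3 numbers as already enrolled, although Protocol 4.1 still speaks of US participants to come. If enrollment is complete, the protocol change may reach few women and the SAP summary carries most of the benefit.
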